#### 6.3.5 Electrocardiogram

A standard 12-lead ECG will be performed with the subject sitting for ≥5 minutes prior to the assessment.

#### 6.3.6 Safety Endpoints

The safety endpoints of interest are:

- Frequency of TEAEs;
- TEAEs leading to discontinuation;
- Treatment-emergent SAEs;
- Percentage of subjects with serum cortisol level  $\leq 5 \mu g/dL$  ( $\leq 138 \text{ nmol/L}$ ) or abnormal ACTH stimulation test (serum cortisol  $\leq 16 \mu g/dL$  [ $\leq 440 \text{ nmol/L}$ ] at 60 minutes);
- The number of subjects discontinuing for HPA axis suppression will be recorded.

Frequency of oral and esophageal candidiasis.

#### 6.4 Pharmacokinetics

Sparse PK sampling (all subjects) will be performed to characterize FP exposure in the study population. PopPK analysis will be performed based on sparse plasma concentration data.

Pharmacokinetic samples will be collected from subjects in all 5 dosing groups to maintain the blind (see Section 5.7). Samples collected from subjects in the placebo dosing group will not be analyzed. Samples collected from subjects in the 1.5 and 3 mg HS, 1.5 and 3 mg BID dosing groups will be analyzed for PopPK results. As part of the PopPK modeling, renal and hepatic function as well as concomitant medications will be considered.

## 6.4.1 Sparse Pharmacokinetic Sampling

Sparse PK samples (all subjects) will be performed in all subjects enrolled in FLUTE. The main study ICF will include consent for sparse PK sampling.

The following PK samples will be collected for all subjects for sparse PK sampling:

- Day 1: pre-dose;
- Week 4, Week 8, and Week 12: Subjects will take their "after breakfast" dose as scheduled on the day of the visit at the site and 2 samples will be taken during their scheduled visit:
  - 1. Subjects must fast approximately 8 hours before the scheduled visits.
  - 2. Upon arrival to the site: After arrival at the site and once samples for serum cortisol and sparse PK are drawn, the subject will eat breakfast and take their "after breakfast" dose approximately 30 minutes after breakfast. There are no requirements for the time duration between when the "after breakfast" dose is administered and this first sample to be collected on-site. The "at bedtime" must not have been taken at the time of sampling.
  - 3. Approximately 1 to 1.5 hours after first sample (immediately prior to leaving the site). This sample must be collected ≥1 hour after the first sample at a given site; there is no maximum time duration between the first and second sample to be collected.

Site staff should document the time of the morning dose. Due to this variability, the sparse PK samples are expected to represent a large portion of the 12-hour post-dosing interval.

#### 6.4.2 Methods for Pharmacokinetic Sampling

Samples of whole blood will be obtained in a Vacutainer® containing sodium fluoride/potassium oxalate anticoagulant for the determination of PF in human plasma.

The following information will be captured for blood sample collection in each subject's eCRF:

- Subject's number;
- Time and date of each blood sample collected for PK analysis;
- Time and date of subject's most recent ingestion of food prior to dose administration;
- Time and date of administration of the "after breakfast" dose (day of the planned visit);
- Time and date of administration of the immediately preceding "at bedtime" dose (evening prior to the planned visit).

If a subject refuses blood collection for PK analysis, this will not be considered a protocol violation as the PK analysis is a secondary objective.

#### 6.4.3 Pharmacokinetic Variables

The following PopPK parameters will be estimated using sparse sampling, as data permit:

- Oral clearance (CL/F);
- Volume of distribution (V/F).

Additional PopPK parameters will be estimated, as appropriate, based on the final structural PK model.

A PopPK approach will be used to analyze sparse PK samples.

# 6.5 Appropriateness of Measurements

All assessments will be performed using methods that are considered standard and appropriate with the exception of the dysphagia instrument which is being developed. Data from FLUTE will provide validation information, such as test-retest validity and responsiveness to change. The instrument will be validated with the results of the current study. Screenshots will be submitted in a separate document.

# 7.0 QUALITY CONTROL AND QUALITY ASSURANCE

According to the Guidelines of Good Clinical Practice (GCP), the Sponsor is responsible for implementing and maintaining quality assurance and quality control systems with written standard operating procedures.

Quality control will be applied to each stage of data handling.

The following steps will be taken to ensure the accuracy, consistency, completeness, and reliability of the data:

- Investigator meeting(s);
- Central laboratories for clinical laboratory parameters and ECGs;
- Site initiation visit;
- Early site visits following enrollment;
- Routine monitoring;
- Ongoing site communication and training;
- Data management quality control checks;
- Continuous data acquisition and cleaning;
- Internal review of data:
- Quality control check of the final clinical study report (CSR).

In addition, Sponsor and/or designee clinical quality assurance department may conduct periodic audits of the study processes, including, but not limited to site, site visits, central laboratories, vendors, clinical database, and final CSR. When audits are conducted, access must be authorized for all study related documents including medical history and concomitant medication documentation to authorized Sponsor representatives and regulatory authorities.

#### 7.1.1 Monitoring

The Sponsor has engaged the services of a CRO to perform all clinical monitoring functions within this clinical study. The CRA will establish and maintain regular contact between the Investigator and the Sponsor.

The CRA will evaluate the competence of each site, informing the Sponsor about any problems relating to facilities, technical equipment, or medical staff. During the study, the CRAs will check that written informed consent has been obtained from all subjects correctly and that data are recorded correctly and completely. The CRAs are also entitled to compare entries in eCRFs with corresponding source data and to inform the Investigator of any errors or omissions. The CRAs will also monitor adherence to the protocol at the site. They will arrange for the supply of study drug and ensure appropriate storage conditions are maintained.

Monitoring visits will be conducted according to all applicable regulatory requirements and standards. Regular monitoring visits will be made to each site while subjects are enrolled in the study. The CRA will make written reports to the Sponsor on each occasion contact with the Investigator is made, regardless of whether it is by phone or in person.

During monitoring visits, entries in the eCRFs will be compared with the original source documents (source data verification). The current study will utilize a Data-driven Trial Execution model; as such, not all data in the eCRF will be source verified.

#### 7.1.1.1 Source Documents

The following are considered to be source data:

- Medical and clinical charts;
- Nursing notes;
- Medical and study-related correspondence regarding the subject;
- Subject progress notes;
- ECG tracings;
- X-ray reports;
- EREFs worksheet;
- Peak eosinophil count;
- Histology results (pdfs);
- Laboratory reports;
- Study worksheets.

In some cases, the eCRF, or part of the eCRF may also be considered source documents. In such cases, a document should be available at the Investigator's site as well as at Adare Pharmaceuticals, and clearly identify those data that will be recorded in the eCRF. The eCRF

will stand as the source for these documents. The eCRFs for the 7-day EEsAI will also be considered as source documents.

All individual entries in the source documents require signatures and dates by the Investigators. All typed or dictated documents and computer printouts must be signed and dated by the Investigator to confirm review. If the site uses electronic (paperless) hospital reporting systems, the CRA must be provided access to verify the source data. In the case that access cannot be provided, the Investigator must sign and date a hard copy of this data for this to be considered a source document

Draft and/or fax copies of laboratory preliminary reports must be initialed and dated, and need to be retained in site files. Final laboratory reports should be signed and dated by the Investigator to confirm review. Original laboratory reports should be kept in site files.

#### 7.1.1.2 Protocol Deviation Definition and Process

A protocol deviation is an excursion (generally unplanned) from the expected conduct of the study that is inconsistent with the protocol, ICF, or study agenda.

At each visit, subjects who fail to adhere to treatment will be assessed on whether or not the lack of adherence to dosing regimen was due to AEs. The Investigator should make every effort to ensure that visits occur at the appropriate intervals.

The Investigator must notify the Medical Monitor and/or clinical study manager of any protocol deviation. Protocol deviations will be documented in the Clinical Trial Management System and evaluated and categorized by the Medical Monitor. Protocol deviations including the reason for any out of window study visits, will be documented in the subject source records.

Protocol deviations must be reported to the IRB/IEC per local requirements.

#### 7.1.2 Data Management and Coding

An EDC system will be used for the study. Data collection will be completed by authorized site staff designated by the Investigator. Appropriate training and security measures will be completed with the Investigator and all authorized site staff prior to the study being initiated and any data being entered into the system for any study subjects.

A completion guideline will be developed to provide guidance to site personnel on how to record data in the eCRF.

All data must be entered in English. The eCRFs should always reflect the latest observations on the subjects participating in the study. Therefore, the eCRFs are to be completed as soon as possible during or after the subject's visit. To avoid inter-observer variability, every effort

APT-1011

should be made to ensure that the same individual who made the initial baseline determinations completes all efficacy and safety evaluations. The Investigator must verify that all data entries in the eCRFs are accurate and correct. If some assessments are not done, or if certain information is not available or not applicable or unknown, the Investigator should indicate this in the eCRF. The Investigator will be required to electronically sign off on the clinical data.

The CRA will review the eCRFs and evaluate them for completeness and consistency. The eCRF will be compared with the source documents to ensure that there are no discrepancies between critical data. All entries, corrections, and alterations are to be made by the responsible Investigator or his/her designee. The CRA cannot enter data in the eCRFs. Once clinical data of the eCRF have been submitted to the central server, corrections to the data fields will be audit trailed, meaning that the reason for change, the name of the person who performed the change, together with time and date will be logged. Roles and rights of the site staff responsible for entering the clinical data into the eCRF will be determined in advance. If additional corrections are needed, the CRA or data manager will raise a query in the EDC application. The appropriate site staff will answer queries sent to the Investigator. This will be audit trailed by the EDC application meaning that the name of site staff, time, and date stamp are captured.

The eCRF is essentially considered a data entry form and should not constitute the original (or source) medical records unless otherwise specified. Source documents are all documents used by the Investigator or hospital that relate to the subject's medical history, that verify the existence of the subject, the inclusion and exclusion criteria, and all records covering the subject's participation in the study. They include laboratory notes, ECG results, memoranda, pharmacy dispensing records, subject files, etc.

The Investigator is responsible for maintaining source documents. These will be made available for inspection by the CRA at each monitoring visit. The Investigator must submit a completed eCRF for each subject who receives study drug, regardless of duration. All supportive documentation submitted with the eCRF, such as laboratory or hospital records, should be clearly identified with the study and randomization number. Any personal information, including subject name, should be removed or rendered illegible to preserve individual confidentiality.

The eCRF records will be automatically appended with the identification of the creator, by means of their unique UserID. Specified records will be electronically signed by the Investigator to document his/her review of the data and acknowledgement that the data are accurate. This will be facilitated by means of the Investigator's unique UserID and password; date and time stamps will be added automatically at time of electronic signature. If an entry on an eCRF requires change, the correction should be made in accordance with the relevant software

procedures. All changes will be fully recorded in a protected audit trail, and a reason for the change will be required.

A detailed Data Management Plan will be developed to ensure the quality of the data. The eCRF will be validated through extensive data checking and query processing capabilities. Capabilities will include generating open queries and routing answers.

#### 7.1.3 Quality Assurance Audit

The Sponsor has instituted a quality assurance program to ensure that all aspects of the study have been conducted according to GCP, International Council for Harmonisation (ICH) guidelines, and applicable laws and regulations. This may include an audit by the Sponsor or designee and/or regulatory agency representatives at any time. The Investigator must agree to the audit of study-related records by regulatory agency and/or the Sponsor or designee and provide direct access to source data/documents along with adequate space to conduct such an audit. The Investigator must adhere to these principles, in addition to any applicable or local requirements.

#### 8.0 STATISTICS

## 8.1 Determination of Sample Size

Part 1 includes a sample size with 100 subjects, in which 20 patients are randomized each to 1.5 mg HS, 1.5 mg BID, 3 mg HS, 3 mg BID, and placebo in the ratio 1:1:1:1:1. See also the discussion of randomization in Section 4.1.5.2.

## 8.1.1 Expected Number of Subjects by Part

The following assumptions were used:

- The 1:1:1:1 (1.5 mg HS: 1.5 mg BID: 3 mg HS, 3 mg BID: placebo) randomization ratios will remain constant throughout the study.
- Based on these randomization ratios, approximately 80% of all subjects in Part 1 will be treated with an APT-1011 dosing regimen and approximately 20% of all subjects in Part 1 will be treated with placebo.
- Based upon the PR-021 study, which had slightly different histologic response criteria, it is expected that approximately 60% of patients on active treatment are expected to be a histologic responder compared to 10% on placebo. The lowest dose may be less effective.
  - Assuming a 60% histologic response rate for the 3 highest active doses of 1.5 mg BID, 3 mg HS, 3 mg BID, a 20% response rate for 1.5 mg HS, and a 10% response rate for placebo, it is expected that overall approximately 50% of active treatment will be responders at Week 12 (40 out of 80).
  - o It is expected that at Week 26 an additional 20% will drop out who were previously responders and of the PART 1 non-responders that 40% will still be non-responders.
  - After Week 26, of the remaining subjects, it is expected that approximately 20% will dropout before Week 52.

Given these assumptions, it is expected that approximately 42 patients will be responders and complete Week 26, and about 34 of those responders will complete Week 52.

The power for testing each active dose versus placebo given a histologic response rate of 60% active treatment and 10% placebo for the primary endpoint (Part 1) is equal to 97.5% (one-sided Type I error = 0.05). Additionally, the power for achieving statistical significance for all 3 of the highest active doses of 1.5 mg BID, 3 mg HS, 3 mg BID via the gatekeeping hypothesis testing approach assuming independence is approximately 0.93.

Due to lack of previous data, estimating power for the secondary endpoint of reduction in number of dysphagia episodes is difficult. We expect that majority of control group will range between 25-35 dysphagia episodes per week at baseline. We expect a placebo effect corresponding to a 20-30% reduction, implying a reduction of 5-10 episodes. If we assume that the range of reduction for patients in control group is 0 to 15 episodes (and a normal distribution), this would correspond to a standard deviation of approximately 15/6=2.5 episodes. We also expect treatment group to also have 25-35 dysphagia episodes per week at baseline, and a reduction of 30-60% with treatment, implying a reduction of 7 to 21 episodes. If we assume that the range of reduction for patients in treatment group is 0 to 30 episodes (and a normal distribution), this would correspond to a standard deviation of approximately 30/6=5 episodes. Given the uncertainty of these estimates, our conservative approach assumes standard deviations of 4.5 and 7.5 for control and treatment group (respectively) for the reduction in number of dysphagia episodes. Given these assumptions, we have 80% power for 20 active dose patients vs. 20 control patients to detect a mean difference in reduction between groups of 5.0 episodes. This calculation is for a single active arm vs. control and does not factor in the multiplicity of having 4 potential doses to test. Assuming independence, a conservative Bonferonni approach would provide 80% power for a mean difference in reduction between groups of 6.3 episodes per arm, indicating the study is powered for an effect size of 5.0 to 6.3 episodes in reduction of dysphagia episodes for each of the doses.

The study has other important objectives which require sufficient sample size. The sample size of a total of 100 subjects as specified for the primary endpoint is considered sufficient to adequately evaluate the measurement properties of the new PRO instrument, and assess the amount of change that is clinically meaningful and to establish cut offs for Response and Relapse.

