## 6.2.8.2 Secondary Efficacy Endpoints

The following secondary efficacy endpoints will be evaluated:

- EoE sustained response: percentage of subjects who met the primary endpoint (histology) at Week 12 and maintained the primary endpoint at Week 26 and Week 52;
- Change from baseline EREFs at Week 12, Week 26, and Week 52;
  - Endoscopic changes will as per the EREFs evaluation based on the following endoscopic features: edema, rings, exudates, furrows, stricture, and several miscellaneous features (crepe paper esophagus, narrow caliber esophagus, and esophageal erosions);
- Percentage of subjects with a peak eosinophils/HPF number <1 and <15 at Week 12, Week 26, and Week 52;

- Change from baseline Global EoE Symptom Score assessed prior to randomization, which will be assessed for the 7-day period prior to the following study visits: Week 4, Week 8, Week 12, Week 14, Week 18, Week 22, Week 26, Week 28, Week 36, Week 44, and Week 52;

- Dysphagia: Change in the number of dysphagia episodes at baseline (14-day period prior to randomization) compared with the 14-day period prior to the time point of interest (Week 12, Week 26 and Week 52).
- Change from baseline 7-day EEsAI total score assessed prior to randomization to those assessed at Week 12, Week 26, and Week 52;
- Change from baseline 7-day EEsAI subscores to those assessed at Week 12, Week 26, and Week 52;
- Percentage of subjects with mean 7-day EEsAI total score <20 to those assessed at Week 12, Week 26, and Week 52;
- Change from baseline PGIS assessed prior to randomization at Weeks 4, 8, 12, 14, 18, 22, 26, 28, 36, 44, and 52;
- PGIC at Weeks 4, 8, 12, 14, 18, 22, 26, 28, 36, 44, and 52.
- Assessment of treatment failure and relapse, including:
  - o Percentage of histologic non-responders by dose at Week 12, Week 26, and Week 52;
  - Percentage of subjects requiring emergency endoscopic food dis-impaction by dose before Week 14, between Week 14 and Week 28, and between Week 28 and Week 52;
  - Percentage of subjects requiring esophageal dilation by dosing group and part of the study.

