Copyright © 2009, 2010, 2012, 2016, 2018 IQVIA. All rights reserved. The contents of this document are confidential and proprietary to IQVIA Holdings Inc. and its subsidiaries. Unauthorized use, disclosure or reproduction is strictly proh bited.

Page 45 of 70

percentages.

No statistical testing will be performed.

16.2.3.4. Analysis of Change from baseline in each of Global EoE Symptom Score, Total EREFs Score, Number of Dysphagia Episodes, 7-day EEsAI total score, 7-day EEsAI VDQ and AMS subscores The change from baseline in each of Global EoE Symptom Score (see section 16.2.1.4), 7-day EEsAI total score (see section 16.2.1.6) and 7-day EEsAI VDQ and AMS subscores (see section 16.2.1.7) will be summarized as continuous variables, and analysis of covariance (ANCOVA) will be used to compare the mean change from baseline in each of the APT-1011 dosing groups to placebo, at the Week 12 visit, with the estimated mean difference, 90% confidence interval of the mean difference and 1-sided p-values provided. This statistical testing at Week 12 is considered descriptive only and no adjustments will be made for multiple comparisons. The ANCOVA models will include the factors described in section 7.1.

All these change from baseline analyses will only include data while subjects are receiving double-blind study drug. Data will not be not included for visits after a histologic non-responder at Week 12 had received single-blind (to subject) APT-1011 3 mg BID in Part 2.

For the analysis of change from baseline in the number of dysphagia episodes (see section 16.2.1.5) and dysphagia free days, for each dose that meets the criterion for statistical significance on the primary efficacy outcome, a Wilcoxon Rank-Sum test will be used to test whether the reduction in the number of dysphagia episodes from baseline is larger for the APT-1011 dosing group compared to the control.

Holm's step-down procedure (Holm, 1979) will be used to control the overall Type I error at 0.05, where the number of doses considered for inferential testing is equal to the number of doses that meet statistical significance for the primary efficacy analysis.

Holm's step down procedure will be implemented as follows:

Let the number of APT-1011 doses that meet statistical significance in the primary efficacy analysis be represented by d (where d is between 1 and 4 inclusive for this study).

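### The dysphagia power figure (80% for 5.0 to 6.3 episodes) is on a weekly scale and reproduces as a t-test, but the endpoint is a 14-day count tested by Wilcoxon rank-sum

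*Protocol*

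**What the plan says.** Protocol section 8.1.1 starts from the expectation that most control subjects will "range between 25-35 dysphagia episodes per week at baseline", and assumes the same range for active treatment. For placebo it writes: "We expect a placebo effect corresponding to a 20-30% reduction, implying a reduction of 5-10 episodes". For active treatment it expects "a reduction of 30-60% with treatment, implying a reduction of 7 to 21 episodes". It derives SDs of 2.5 (control) and 5 (active) from assumed ranges of reduction, then inflates them to 4.5 and 7.5 as a conservative choice. With 20 subjects per arm it claims 80% power for a difference of 5.0 episodes in a single comparison, and for 6.3 episodes after a Bonferroni adjustment for four doses, "indicating the study is powered for an effect size of 5.0 to 6.3 episodes". The paragraph names no test, no sidedness and no time unit for these two figures.

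Protocol section 6.2.8.2 defines the endpoint over a different window: the 14 days before randomization "compared with the 14-day period prior to the time point of interest". SAP section 16.2.1.5 likewise sums real-time events over the previous 14 days. For the analysis, SAP section 16.2.3.4 states that "a Wilcoxon Rank-Sum test will be used to test whether the reduction in the number of dysphagia episodes" is larger on active treatment, with Holm's procedure applied across the doses that succeed on the primary endpoint. Protocol section 8.8.3 says the same. SAP section 6.6 makes all tests one-sided at 5%.

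**The concern.** A power statement should be in the units of the endpoint and for the planned test. This one appears to be in neither. The Week 12 result will be reported as a difference in 14-day counts, and the nearest benchmark in the protocol is a bare 5.0 to 6.3 episodes. A reader who puts the two together could be wrong by a factor of up to two about what the trial was sized to detect, and could misread a null result.

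This matters more here than for the other secondary endpoints. The number of dysphagia episodes is the one for which protocol section 8.8.3 and SAP section 7.4 plan formal testing with control of Type I error; p-values for the rest are descriptive.

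**Working it through.** **Inputs.** From protocol section 8.1.1: SDs 4.5 and 7.5, n = 20 per arm, differences 5.0 and 6.3, four doses. From SAP section 6.6: one-sided 5%. The Bonferroni level is 0.05/4 = 0.0125, which is also Holm's first step when all four doses pass the primary endpoint.

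**1. The unit is weekly.** 20% of 25 = 5 and 30% of 35 = 10.5, against the stated 5-10. 30% of 25 = 7.5 and 60% of 35 = 21, against the stated 7-21. The reductions are percentages of the weekly baseline, and the SDs are built around reductions of that size.

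**2. Reproducing the stated power.**

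- SE = √(4.5²/20 + 7.5²/20) = √3.825 = 1.956.
- Noncentrality: 5.0/1.956 = 2.56 and 6.3/1.956 = 3.22.

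| Noncentral t | 5.0, alpha 0.05 | 6.3, alpha 0.0125 |
|---|---|---|
| One-sided, unequal variance | 80.4% | 80.2% |
| One-sided, pooled | 80.7% | 80.9% |
| Two-sided, pooled | 70.3% | 72.3% |

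The unequal-variance differences giving exactly 80% are 4.97 and 6.29. The stated figures are therefore a one-sided two-sample t-test on weekly counts with all 20 per arm evaluable. The t-test is inferred from this match.

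**3. The planned test on the same weekly inputs.** Simulated one-sided Wilcoxon rank-sum power, with normally distributed reductions as the protocol assumes:

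| | 5.0, alpha 0.05 | 6.3, alpha 0.0125 |
|---|---|---|
| 20 per arm | 77-79% | 77-78% |
| 18 per arm (assumed 10% loss) | 74-75% | 72-73% |
| Difference for 80% power, 20 per arm | about 5.1-5.2 | about 6.5 |

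The ranges cover the test with and without continuity correction and, at 20 per arm, reductions rounded to whole episodes. The documents give no dropout rate before Week 12, so 18 per arm is illustrative. Protocol section 4.1.1 does have subjects with food impaction leave the study, and SAP section 16.2.1.5 gives no rule for a missing Week 12 count.

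**4. Conversion to 14 days.** The documents give no 14-day SD. A 14-day reduction is the sum of two weekly reductions, so its SD lies between √2 times the weekly SD (uncorrelated weeks) and 2 times (perfectly correlated weeks). The t-test differences for 80% power scale in the same way:

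- alpha 0.05: 4.97 × √2 = 7.03 to 4.97 × 2 = 9.94;
- alpha 0.0125: 6.29 × √2 = 8.89 to 6.29 × 2 = 12.57.

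**5. Does the change of unit lower power?** A sustained weekly effect doubles over 14 days: 5.0 × 2 = 10.0 and 6.3 × 2 = 12.6.

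| 14-day SD | Test | 10.0, alpha 0.05 | 12.6, alpha 0.0125 |
|---|---|---|---|
| 2 × weekly | t (unequal variance) | 80.4% | 80.2% |
| 2 × weekly | Wilcoxon | 78-79% | 77-78% |
| √2 × weekly | t (unequal variance) | 97.1% | 98.3% |
| √2 × weekly | Wilcoxon | 96% | 98% |

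Power is unchanged or higher. Only if 5.0 and 6.3 are themselves taken as 14-day differences does Wilcoxon power fall, to 33-54% and 23-46%.

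**The case against.** A reader might infer from the low figures at the end of the working that the stated power is not delivered. The documents do not support that. Those figures enlarge the SD to 14 days but leave the effect at its weekly size, whereas section 8.1.1 derives both from weekly counts. Converted to weekly terms, the 14-day detectable differences are 7.03/2 = 3.5 to 4.97 and 8.89/2 = 4.4 to 6.29, no worse than stated. The midpoints of the protocol's expected reductions (7.5 and 14) differ by 6.5 per week, or 13 over 14 days, which exceeds even 12.57. That argument stands.

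It can also be said that the change of test costs only 2-3 points; that the inflated SDs leave a margin (with 2.5 and 5, Wilcoxon power at 5.0 is 98% with 20 per arm and 97% with 18); that Holm is never less powerful than Bonferroni; and that the protocol admits this power is hard to estimate and sizes the trial on the primary endpoint. All of this is fair and limits the consequence. It does not supply the missing unit or test: the admitted uncertainty concerns the inputs, and the margin applies only if the smaller SDs are true.

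**Conclusion.** The concern holds as a mismatch between the stated power and the endpoint it describes. On the protocol's own SDs and scale, the planned test gives about 77-79% where 80% is claimed. The detectable differences at 80% become about 5.1-5.2 and 6.5 episodes per week in place of 5.0 and 6.3, and power is lower if Week 12 diaries are missing. In the endpoint's own units the corresponding t-test differences are about 7.0-9.9 and 8.9-12.6.

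This is not a finding that the trial is underpowered for a sustained weekly effect. The result rests on three things: the weekly unit and the t-test, both inferred from the inputs and the reproduction; normally distributed reductions, where skewed counts could move Wilcoxon power either way; and a 14-day SD assumed at √2 to 2 times the weekly value.

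**What to change.** In protocol section 8.1.1, do one of the following:

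- label 5.0 to 6.3 as episodes per week, and define the analysed endpoint in protocol section 6.2.8.2 and SAP section 16.2.1.5 as mean weekly episodes over the 14 days; or
- keep the 14-day count and restate the effect, SD and detectable difference for it, with the assumed link between weekly and 14-day SD shown.

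In either case name the test, state that it is one-sided, and quote Wilcoxon power at the Holm levels, preferably with an expected number evaluable at Week 12. No extra patients are needed. The cost is a revised paragraph (plus a changed endpoint definition under the first option) and a slightly less favourable stated figure.
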